5.3 ASSESSMENT OF SAFETY

5.3.1 Physical examination

At start of run-in and end of treatment, a complete physical examination will be performed by the investigator (see [Flow chart](#)). Documentation of, and findings from the physical examination, must be part of the source documents available at the site.

5.3.2 Vital Signs

Systolic and diastolic blood pressure as well as pulse rate (electronically or by palpation, count for 1 minute) will be measured after 5 minutes of rest in the seated position. All recordings should be made using the same blood pressure recording instrument on the same arm (see Flow chart).

5.3.3 Safety laboratory parameters

All safety laboratory samples (except at Visit 1) will be collected after a full overnight fast (nothing to eat or drink except water for at least 10 hours) and before background anti-diabetic therapies and investigational drug as described in the Flow Chart and [Section 6](#). The blood sample at Visit 1 (screening visit) can be taken with the patient in a fasted or non-fasted state.

All parameters that will be determined during the trial conduct are listed in [table 5.3.3: 1](#) and [5.3.3: 2](#). The analysis will be performed by a central laboratory. The respective reference range and details about sample handling and shipment will be provided in the ISF (Lab Manual).

Reduced safety lab panels excluding urinalysis are planned for the following visits:

- For the screening Visit 1, laboratory only includes liver transaminases, alkaline phosphatase, and serum creatinine.

- Lipid fractions will only be determined at baseline (V3) and end of treatment (V8)

Table 5.3.3: 1 Safety laboratory parameters – Haematology

-
- Haematocrit
 - Haemoglobin
 - Red Blood Cells (RBC)/Erythrocytes
 - WBC/Leukocytes
 - Platelet Count/Thrombocytes
 - Differential Automatic (relative and absolute count):
 - Neutrophils, Eosinophils, Basophils, Monocytes, Lymphocytes
-

Table 5.3.3: 2 Safety laboratory parameters – Clinical Chemistry

-
- | | |
|---|--|
| 
 • Amylase • Lipase • AST (aspartate transaminase, SGOT) • ALT (alanine transaminase, SGPT) • γ-GT (gamma-glutamyl-transferase) • Alkaline phosphatase • Lactic dehydrogenase (LDH) • Total bilirubin • Direct bilirubin, if total bilirubin is elevated • Total Protein • Albumin • Creatine kinase (CK) • CK-MB, if CK is elevated | 
 • Potassium • Sodium • Creatinine • Urea • Calcium • Inorganic phosphorous • Uric acid • Cholesterol (total) * • HDL cholesterol* • LDL cholesterol* • Triglycerides* • Glucose |
|---|--|
- * Visits 3,8 only
-

Table 5.3.3:3 Safety laboratory parameters – urine

-
- | | |
|--|--|
| 
 • Albumin, Creatinine (spot urine –quantitative measurement) • Protein • Glucose | 
 • Ketone • Leucocytes • Erythrocytes |
|--|--|
-

The albumine/creatinine ratio will be calculated at the central lab. Urine sediment will only be done if there is a positive finding on the urinalysis.

The glomerular filtration rate (GFR) will be derived from serum creatinine* values based on the standard MDRD formula:

$$\text{eGFR (ml/min/1.73 m}^2\text{)} = 175 \times [\text{Screatinine (umol/L)/88.4}]^{-1.154} \times [\text{age}]^{-0.203} \times [0.742 \text{ if patient is female}] \times [1.212 \text{ if patient is of African origin}]$$

*: creatinine methods calibrated to an IDMS reference method

Pregnancy testing (urine) will be performed in female patients of child bearing potential only according to the timepoints indicated in the [Flow chart](#).

5.3.4 Electrocardiogram

Printed paper traces from 12 lead ECGs (I, II, III, aVR, aVL, aVF, V1-V6) will be collected at baseline (visit 3) and at the end of the trial (visit 8) for all patients. In the event of any cardiac symptoms (i.e. suspicion of heart rhythm disorders or cardiac ischemia), an additional ECG will be recorded. All ECGs will be evaluated, (signed, dated and commented upon) by the treating physician/investigator and stored locally.

Any clinically relevant changes in the ECG will be reported as AEs. Any ECG abnormalities will be carefully monitored and if necessary the patient will be removed from the trial and medically treated.

5.3.5 Other safety parameters

Home Blood Glucose Monitoring

All patients will be provided with HBGM equipment and supplies for use at home during the 2-week Run-In periods. Instruction on the proper use of the HBGM will be provided by the study staff. The patient will be asked to record the results of the HBGM test on a HBGM Testing Log that will be included in the patients source document file. Only in the case of linked adverse events or of hypoglycaemia, the single HBGM values will be recorded in the CRF.

During Run-In and Follow-up, HBGM testing should be performed once daily in the fasted state and at any time the patient is symptomatic, i.e., experiences signs/symptoms of hyper- or hypoglycaemia. If during Run-in, results of a HBGM test reveal blood glucose >240 mg/dL (13.3 mmol/L) after an overnight fast, the patient should contact the site. The investigator should then decide about start of the randomised period or further patient participation in the trial based on fasted plasma glucose determinations according to the inclusion and exclusion criteria as outlined in [Section 3.3](#).

During the randomised treatment period, HBGM testing is recommended to be done once weekly (more frequently if required by local authorities) and at any time the patient is symptomatic, i.e., experiences signs/symptoms of hyper- or hypoglycaemia. If during this period, results of a fasting HBGM test reveal blood glucose levels meeting rescue criteria (see [Section 4.2.1](#)), the patient should contact the site and the investigator should follow the instructions given in Section 4.2.1.

5.3.6 Assessment of adverse events

5.3.6.1 Definitions of AEs

Adverse event

An adverse event (AE) is defined as any untoward medical occurrence in a patient or clinical investigation subject administered a medicinal product and which does not necessarily have to have a causal relationship with this treatment.

An AE can therefore be any unfavourable and unintended sign (including an abnormal laboratory finding), symptom, or disease temporally associated with the use of a medicinal product, whether or not considered related to the medicinal product.

Adverse reaction

An adverse reaction is defined as a response to a medicinal product which is noxious and unintended. Response in this context means that a causal relationship between a medicinal product and an adverse event is at least a reasonable possibility. Adverse reactions may arise from use of the product within or outside the terms of the marketing authorisation or from occupational exposure. Conditions of use outside the marketing authorization include off-label use, overdose, misuse, abuse and medication errors.

Serious adverse event

A serious adverse event (SAE) is defined as any AE which:

- results in death,
- is life-threatening, this refers to an event in which the patient was at risk of death at the time of the event; it does not refer to an event that hypothetically might have caused death if more severe.
- requires inpatient hospitalisation or
- prolongation of existing hospitalisation,
- results in persistent or significant disability or incapacity, or
- is a congenital anomaly / birth defect,
or
- is to be deemed serious for any other reason if it is an important medical event when based upon appropriate medical judgment which may jeopardise the patient and may require medical or surgical intervention to prevent one of the other outcomes listed in the above definitions.

Medical and scientific judgement should be exercised in deciding whether other situations should be considered serious reactions, such as important medical events that might not be immediately life threatening or result in death or hospitalisation but might jeopardise the patient or might require intervention to prevent one of the other outcomes listed above. Examples of such events are intensive treatment in an emergency room or at home for allergic bronchospasm, blood dyscrasias or convulsions that do not result in hospitalisation or development of dependency or abuse. Any suspected transmission via a medicinal product of an infectious agent is also considered a serious adverse reaction.

AEs considered “Always Serious”

Cancers of new histology and exacerbations of existing cancer must be reported as a serious event regardless of the duration between discontinuation of the drug and the occurrence of the cancer.

In accordance with the European Medicines Agency initiative on Important Medical Events, Boehringer Ingelheim has set up a list of further AEs, which by their nature, can always be considered to be “serious” even though they may not have met the criteria of an SAE as given above.

The latest list of “Always Serious AEs” can be found in the Remote Data Capture (RDC) system. These events should always be reported as SAEs as described above.

Adverse events of special interest (AESIs)

The term AESI relates to any specific AE that has been identified at the project level as being of particular concern for prospective safety monitoring and safety assessment within this trial, e.g. the potential for AEs based on knowledge from other compounds in the same class. AESI need to be reported to the sponsor’s Pharmacovigilance Department within the same timeframe that applies to SAE, please see above.

The following are considered as AESIs:

- Hypersensitivity reactions such as angioedema, angioedema-like events, and anaphylaxis
- Skin lesions such as exfoliative rash, skin necrosis, or bullous dermatitis
- *Hepatic injury as defined by the following alterations of hepatic laboratory parameters: ≥ 3 fold ULN of AST and/or ALT in combination with an elevation of total bilirubin > 2 fold ULN measured in the same blood draw sample, hepatitis, hepatic injury, jaundice and potential Hy’s Law cases
- Renal adverse events such as acute renal failure
- Pancreatitis (refer to the ISF)
- Pancreatic cancer

*These lab findings constitute a hepatic injury alert and the patients showing these lab abnormalities need to be followed up according to the “DILI checklist” provided via RDC. In case of clinical symptoms of hepatic injury (icterus, unexplained encephalopathy, unexplained coagulopathy, right upper quadrant abdominal pain, etc.) without lab results (ALT, AST, total bilirubin) available, the Investigator should make sure these parameters are analysed, if necessary in an unscheduled blood test. Should the results meet the criteria of hepatic injury alert, the procedures described in the DILI checklist should be followed.

Protocol-specified AESIs (as identified by the investigator based on the above definitions for adverse events of special interest) can be classified as serious or non-serious but all these AESIs once identified by the investigator must be reported on an SAE form in an expedited manner similar to SAEs, even if they do not meet any of the SAE seriousness criteria.

Beyond of this, and for the purposes of ongoing pharmacovigilance activities by the sponsor, adverse events based on additional searches for coded preferred terms of adverse events captured in the trial database (such as Special MedDRA Queries (SMQs), and user defined

searches (Boehringer Ingelheim customized MedDRA Queries (BicMQs)) will be queried to verify with the investigator if the adverse event reported represent a suspected or diagnosed protocol specified AESI. AESIs once identified by the investigator must be reported on an SAE form in an expedited manner similar to SAEs, even if they do not meet any of the SAE seriousness criteria.

These additional searches (summarised under the so called ‘overview of protocol defined AESIs and safety topics of interest ’) may change according to active pharmacovigilance of linagliptin. The most up to date list of these searches will be included in the ISF/ RDC system and changes will be communicated to all investigators.

Intensity of AEs

The intensity of the AE should be judged based on the following:

Mild:	Awareness of signs or symptoms that is/are easily tolerated
Moderate:	Enough discomfort to cause interference with usual activity
Severe:	Incapacitating or causing inability to work or to perform usual activities

Causal relationship of AEs

The definition of an adverse reaction implies at least a reasonable possibility of a causal relationship between a suspected medicinal product and an adverse event. An adverse reaction, in contrast to an adverse event, is characterised by the fact that a causal relationship between a medicinal product and an occurrence is suspected.

Medical judgment should be used to determine the relationship, considering all relevant factors, including pattern of reaction, temporal relationship, de-challenge or re-challenge, confounding factors such as concomitant medication, concomitant diseases and relevant history.

Arguments that may suggest that there is a reasonable possibility of a causal relationship could be:

- The event is consistent with the known pharmacology of the drug
- The event is known to be caused by or attributed to the drug class.
- A plausible time to onset of the event relative to the time of drug exposure.
- Evidence that the event is reproducible when the drug is re-introduced
- No medically sound alternative aetiologies that could explain the event (e.g. pre-existing or concomitant diseases, or co-medications).
- The event is typically drug-related and infrequent in the general population not exposed to drugs (e.g. Stevens-Johnson syndrome).
- An indication of dose-response (i.e. greater effect size if the dose is increased, smaller effect size if dose is diminished).

Arguments that may suggest that there is no reasonable possibility of a causal relationship could be:

- No plausible time to onset of the event relative to the time of drug exposure is evident (e.g. pre-treatment cases, diagnosis of cancer or chronic disease within days / weeks

of drug administration; an allergic reaction weeks after discontinuation of the drug concerned)

- Continuation of the event despite the withdrawal of the medication, taking into account the pharmacological properties of the compound (e.g. after 5 half-lives). Of note, this criterion may not be applicable to events whose time course is prolonged despite removing the original trigger.
- Additional arguments amongst those stated before, like alternative explanation (e.g. situations where other drugs or underlying diseases appear to provide a more likely explanation for the observed event than the drug concerned).
- Disappearance of the event even though the study drug treatment continues or remains unchanged.

5.3.6.2 Adverse event collection and reporting

AE Collection

The Investigator shall maintain and keep detailed records of all AEs in their patient files.

The following must be collected and documented on the appropriate CRF by the Investigator:

- From signing the informed consent onwards through the Residual Effect Period (REP), until individual patient's end of trial:

-all AEs (serious and non-serious) and all AESIs.

However, if an individual patient discontinues trial medication prematurely but stays in the trial (i.e. if further visits incl. telephone visits, or vital status assessments are planned) from then on and until the individual patient's end of the trial the Investigator must report related SAEs and related AESIs.

- After the individual patient's end of trial:

the Investigator does not need to actively monitor the patient for AEs but should only report relevant SAEs and relevant AESIs of which the Investigator may become aware of.

[figure not shown]

Figure 5.3.6.2: 1 Types of AEs to be reported according to the trial period

The REP is defined as 7 days after the last trial medication application. All AEs which occurred through the treatment phase and throughout the REP will be considered as on

treatment, please see [section 7.3.4](#). Events which occurred after the REP will be considered as post treatment events.

AE reporting to sponsor and timelines

The Investigator must report SAEs, AESIs, and non-serious AEs which are relevant for the reported SAE or AESI, on the BI SAE form via fax immediately (within 24 hours) to the sponsor's unique entry point (country specific contact details will be provided in the ISF). The same timeline applies if follow-up information becomes available. In specific occasions the Investigator could inform the sponsor upfront via telephone. This does not replace the requirement to complete and fax the BI SAE form.

With receipt of any further information to these events, a follow-up SAE form has to be provided. For follow-up information the same rules and timeline apply as for initial information.

Information required

For each AE, the Investigator should provide the information requested on the appropriate CRF pages and the BI SAE form. The Investigator should determine the causal relationship to the trial medication and any possible interactions between the investigational drug and an AMP.

The following should also be recorded as an (S)AE in the CRF and SAE form (if applicable):

- Worsening of the underlying disease or of other pre-existing conditions
- Changes in vital signs, ECG, physical examination and laboratory test results, if they are judged clinically relevant by the Investigator.

If such abnormalities already pre-exist prior trial inclusion they will be considered as baseline conditions.

All (S)AEs, including those persisting after individual patient's end of trial must be followed up until they have resolved, have been sufficiently characterised, or no further information can be obtained.

Pregnancy

In rare cases pregnancy may occur in a clinical trial. Once a patient has been enrolled into this clinical trial and has taken trial medication, the Investigator must report immediately (within 24 hours) a potential drug exposure during pregnancy (DEDP) to the sponsor's unique entry point (country-specific contact details will be provided in the ISF). The Pregnancy Monitoring Form for Clinical Trials (Part A) should be used.

The outcome of the pregnancy associated with the drug exposure during pregnancy must be followed up and reported to the sponsor's unique entry point on the Pregnancy Monitoring Form for Clinical Trials (Part B).

The ISF will contain the Pregnancy Monitoring Form for Clinical Trials (Part A and B).

As pregnancy itself is not to be reported as an AE, in the absence of an accompanying SAE and/or AESI, only the Pregnancy Monitoring Form for Clinical Trials and not the SAE form

is to be completed. If there is an SAE and/or AESI associated with the pregnancy an SAE form must be completed in addition.

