3. DESCRIPTION OF DESIGN AND TRIAL POPULATION

3.1 OVERALL TRIAL DESIGN AND PLAN

This randomised, double-blind, multi-centre, and placebo-controlled, parallel group study compares linagliptin (5 mg) to placebo as add-on therapy to stable insulin alone (basal insulin, premixed insulin) or in combination with metformin.

In total, 206 patients with T2DM who meet the entry criteria are planned for inclusion in this trial. The randomised treatment will be double-blind between linagliptin and placebo, i.e. each patient will receive either active treatment or placebo matching linagliptin.

Patients pre-treated with insulin alone or insulin in combination with metformin are included in the study once they have signed the informed consent. Acceptable basal insulins could be insulin glargin, insulin detemir or NPH (neutral protamin hagedorn) insulin with duration of action up to 24 h; Furthermore, patients on pre-mixed insulins may be included up to a certain limit in accordance with the defined randomisation criteria (ref. to [section 7.6](#) and the Investigator Site File (ISF) for further details). Acceptable pre-mixed insulins could be preparations with 25/75 or 30/70 ratio, with once or twice daily posology only. All patients suitable after screening will undergo a 2-week placebo run-in period before randomisation. Patients who successfully complete this period and who still meet the inclusion/exclusion criteria will be randomised (with an allocation of 1:1 and refer to section 7.6) to the 24 week randomised treatment period of the study in which they will receive either 5mg linagliptin or placebo. During the 24-week randomised treatment period, the background therapy described above should remain unchanged if at all possible.

The end of treatment (EOT) visit will be performed for all patients upon completion of 24-week treatment and for those who prematurely discontinue trial medication. The follow-up visit will be performed one week after EOT.

The patient participation is concluded when they have undergone last planned visit. The time period for which AEs will still be considered on-treatment is 7 days following last intake of trial medication. After trial completion all AEs, including those persisting are followed-up for up to 30 days and it should be confirmed if they have resolved or sufficiently characterised.

The end of the trial is defined as “last patient out”, i.e. last visit completed by last patient.

[figure not shown]

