6.2.2 Treatment period

The treatment period is from Visit 3 to Visit 8. Patients will be dispensed medication at each of these visits (except for Visit 8). Medication number of each occasion will be allocated by IRT (refer to IRT user manual).

Patients should not take study medication at home on the morning of trial visits during the treatment period.

Randomisation visit (Visit 3)

Visits should be performed fasting and as indicated in the [Flow Chart](#) and the respective protocol sections.

Randomisation/treatment allocation and dispensing of study medication should be the last activity at this visit.

Visits 4-8

Visits should be performed as mentioned in the Flow Chart and the respective protocol sections.

If a patient prematurely discontinues from the 24-week treatment period, the patient must return to the trial site for both Visit 8 (within 7 days of stopping study treatment) and Visit 9 (7 days after Visit 8), which will be performed.

The investigator may initiate any additional antidiabetic therapy for the patient, based on his or her discretion, no sooner than one day after discontinuing study medication or after Visit 8.

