6.2.3 Follow Up Period and Trial Completion

For all patients completing the study according to protocol a follow-up contact (Visit 9) with the patient (preferably by phone) should be done by the investigator at the end of the follow-up period of 7 days.

In case of premature discontinuation from the 24 week treatment period however, an End of Trial Visit (V9) should be performed and the patient should return to Visit 9 (7 days after Visit 8/end of treatment). The following examinations should be performed at Visit 9:

- Vital signs
- Collection of blood and urine samples for safety laboratory evaluation
- Documentation of any adverse events
- Documentation of concomitant therapies

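### Protocol 5.3.6.2 appears to narrow adverse event reporting for early stoppers from the day drug stops, inside the 7-day window that the safety analysis counts as on treatment

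*Protocol*

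**What the plan says.** Protocol 5.3.6.2, under its heading on AE collection, first requires all AEs, serious or not, and all AESIs to go on the CRF from consent through the REP until the patient's end of trial. A sentence beginning with *However* then makes an exception "if an individual patient discontinues trial medication prematurely but stays in the trial", which it explains as having further visits or contacts planned. From that moment until the individual patient's "end of the trial the Investigator must report related SAEs and related AESIs".

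The section sets the REP at 7 days after the last dose and counts as on treatment "All AEs which occurred through the treatment phase and throughout the REP". Protocol 3.1 agrees: "The time period for which AEs will still be considered on-treatment is 7 days following last intake of trial medication". Protocol 7.3.4 and SAP 7.8.1 use the same window. None of them makes an exception for early stoppers.

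Early stoppers have visits planned after the stop. Section 3.1 schedules the end-of-treatment visit for completers "and for those who prematurely discontinue trial medication". Section 6.2.2 has early stoppers "return to the trial site for both Visit 8 (within 7 days of stopping study treatment) and Visit 9", the latter a week after Visit 8. Section 6.2.3 says the "patient should return to Visit 9 (7 days after Visit 8/end of treatment") and lists the documentation of any AE among the Visit 9 tasks. Flow chart note B lists AEs for the same visit, and the flow chart's AE row is marked at Visits 8 and 9.

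**The concern.** The safety tables assign to randomised treatment every recorded AE up to 7 days after the last dose. If the collection rule is narrower in those days for early stoppers than for completers, a treatment-emergent count mixes two standards of capture. If early stopping also differed between arms, the shortfall would differ between arms. A further problem is that a site following 5.3.6.2 to the letter and a site following 6.2.3 would enter different events for the same kind of patient.

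**Working it through.** **Does the sentence narrow the rule?** It does not contain the word *only*. But it sits under the collection heading, follows an all-AE rule and opens with *However*. Related SAEs and related AESIs already fall within all AEs, so the sentence has no function unless it narrows the duty.

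**Which days does it cover?** Count the last dose as day 0.
- REP: days 1 to 7 (Protocol 5.3.6.2, 7.3.4).
- Start of the exception: the drug stop, not the end of the REP.
- Visit 8: day 0 to 7 (6.2.2).
- Visit 9: Visit 8 + 7 = day 7 to 14 (6.2.2), or day 7 if counted from end of treatment (6.2.3).
- End of the exception: the patient's end of trial, which is Visit 9.

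On either reading Visit 9 is not before day 7, so all 7 of 7 REP days fall under the narrower rule for a patient who keeps to the schedule. Because Visits 8 and 9 are planned for every early stopper, each one who agrees to attend meets the condition for the exception.

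**What do other sections still require in those days?**

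| Event in the REP of an early stopper | Other rule, none with an early-stopper exception |
|---|---|
| SAE, related or not | 5.3.6.2, sponsor-reporting paragraph: within 24 hours |
| AESI, related or not | The same paragraph, and 5.3.6.1 |
| Events on the always-serious list, cancers | 5.3.6.1 |
| Clinically relevant vital-sign, ECG, examination or laboratory change | 5.3.6.2 (information required); 5.3.4 for ECG |
| Hypoglycaemia | 5.3.7 |
| Other non-serious, non-AESI event | Visit 9 instruction in 6.2.3, note B and the flow chart AE row, against the *However* sentence |

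The last row is where the contradiction mainly bites.

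**How many patients?** The only rate in the documents is the 2.2% dropout that Protocol 7.7 cites from another trial. Assume that it applies to early drug stopping with continued visits:
- 206 × 0.022 = 4.5, about 5 patients, both arms together.
- At an assumed 10%: 206 × 0.10 = 20.6, about 21 patients.

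SAP 7.8.1 counts patients with an AE, not AEs. A table therefore changes only if an early stopper's first event of that kind falls in those 7 days and is not recorded. With an assumed chance of 2% to 10% per early stopper, the expected number missing from a table is:
- 5 × 0.02 = 0.1 to 5 × 0.10 = 0.5 with 5 stoppers.
- 21 × 0.02 = 0.4 to 21 × 0.10 = 2.1 with 21 stoppers.

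For scale, one missed patient in one arm is 1/103 = 0.97 percentage points.

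**The case against.** The strongest reply is that one sentence is out of line with many instructions that point the other way, so a site following the visit schedule would collect the events anyway. Section 6.2.3 is written for early stoppers and asks for any AE at Visit 9. Section 5.3.6.2 itself tells investigators to "maintain and keep detailed records of all AEs in their patient files". The main collection bullet expressly runs through the REP. The next bullet, on the time after the patient's end of trial, does use *only*, which suggests that the drafter wrote *only* where a limit was meant. Figure 5.3.6.2: 1 addresses which AEs are reported in which period. It cannot be seen here, but investigators have it.

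Much of this stands, and it limits the size of the point. It does not remove the contradiction. The exception still starts at drug stop, and if the figure shows full collection through the REP, the prose disagrees with the figure.

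Three stronger readings are tempting and are not supported:
- A reader might infer that unrelated SAEs and AESIs in the REP may go unreported. The sponsor-reporting paragraph of 5.3.6.2 and section 5.3.6.1 require them without regard to relatedness.
- A reader might see a further conflict with SAP 7.8.4 and 7.8.5.1. Those sections only classify significant new end-of-treatment findings as AEs, and they agree with Protocol 5.3.4 and 5.3.6.2.
- A reader might conclude that the SAP assumes complete capture in this window. SAP 7.8.1 only assigns AEs to treatment by date.

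**Conclusion.** The point holds as a minor inconsistency in data collection. Read in context, the *However* sentence in 5.3.6.2 limits reporting for early stoppers throughout a window that Protocol 3.1, 5.3.6.2 and 7.3.4 and SAP 7.8.1 count as on treatment. It contradicts 6.2.3 and the flow chart, and it fits badly with the unrestricted SAE and AESI rules.

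The practical gap is mainly other non-serious, non-AESI events, in about 5 of 206 patients on the 2.2% assumption, with 0.1 to 0.5 patients expected to be missing from a table. The larger figure of 2.1 needs two assumed inputs, 10% stopping and a 10% chance of a missed event, and neither is in the documents. The number concerned would be lower if some early stoppers leave with no further visits, since post-stop procedures depend on the patient's agreement (Protocol 3.3.4.1). AEs that lead to stopping begin before the stop and are captured under the full rule.

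The safety analysis is descriptive (Protocol 7.3.4, SAP 7.8), and the primary endpoint is unaffected. The reading depends on the prose alone, because the figure is not visible.

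**What to change.** Check Figure 5.3.6.2: 1 first. Then reconcile 5.3.6.2 with 6.2.3, flow chart note B, 7.3.4 and the figure. State that in patients who stop drug early all AEs are collected through the end of the 7-day REP and documented at Visit 9 as 6.2.3 already asks, and that the limit to related SAEs and related AESIs applies only after the REP.

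The cost is one protocol clause, plus the figure if it differs. No visit is added, because early stoppers are already asked to attend Visits 8 and 9. A few more AE entries in the eCRF may follow. The analysis rules in 7.3.4 and SAP 7.8.1 stay as they are.
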